7.5 Safety Monitoring Rules

In addition to the standard monitoring of clinical safety parameters, the following guidelines are provided for the monitoring of selected parameters chosen based on preclinical and clinical observations. For the purposes of safety monitoring baseline is defined as the average of Day 1 pre-dose assessment and the last measurement prior to Day 1.

Confirmation Guidance: At any time during the Study (Treatment or Post-Treatment Periods), the initial clinical laboratory results meeting the safety monitoring criteria presented below **must be confirmed** by performing measurements (ideally in the same laboratory that performed the initial measurement) on new specimens. All new specimen collections should take place as soon as possible (ideally within 3 days of the initial collection). For stopping rules, if the initial laboratory result is observed during the Treatment Period, the results from the retest **must be available** prior to administering the next dose of Study Drug (ISIS 304801 or placebo).

Re-dosing Guidance: Patients with initial laboratory test values that reach a stopping rule must not be re-dosed until the re-test results are available. In general, patients who do not meet the stopping rules based upon retest may continue dosing. However, the Investigator will decide whether additional close monitoring of the patient is appropriate. If any of the stopping criteria described below are met below and are confirmed, the patient will be permanently discontinued from further treatment with Study Drug (ISIS 304801 or placebo), evaluated fully as outlined below and will be entered into the post-treatment evaluation portion of the study. Consultation will be conducted between the Investigator and the Ionis Medical Advisor as needed.

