7.6.3 Stopping Rule for Platelet Count Results

In the event of a confirmed platelet count less than 75,000/mm³ that is associated with major bleeding or clinically relevant non-major bleeding (defined below⁵³), dosing of a patient with study drug (ISIS 304801 or placebo) will be stopped permanently. The follow-up schedule for any events meeting this stopping criterion will be determined by the Investigator in consultation with the Sponsor Medical Monitor as needed.

In the event of any platelet count less than 25,000/mm³, or a platelet count less than 50,000/mm³ that occurs while the patient is on dosing at 300 mg every two weeks or 150 mg every week then dosing of a patient with Study Drug (ISIS 304801 or placebo) will be stopped permanently. Platelet count will be monitored daily until 2 successive values show improvement then monitored every 2-3 days until 2 successive values are > 75kmm³, then monitored every 1 week.

Administration of steroids is recommended for patients whose platelet count is less than $\leq 50K/mm^3$. Recovery in platelet count may be accelerated by administration of high dose steroids. Treatment guidelines for immune thrombocytopenia (Provan et al.; 2010) recommend Dexamethasone 40 mg daily for 4 days every 2-4 wk for 1-4 cycles; Prednis(ol)one 0.5-2 mg/kg/d for 2-4 weeks then taper; or Methylprednisolone 30 mg/kg/day for 7 days (**note:** may require continuation with oral steroids after methyl prednisolone).

In the event of a confirmed platelet count less than 75,000/mm³, and in the absence of major bleeding or clinically relevant non-major bleeding (defined below⁵³), dosing of a patient with study drug (ISIS 304801 or placebo) will be suspended temporarily until the platelet count has recovered to $\geq 100,000/mm^3$. If dosing is continued it should be at a reduced dose frequency of 300 mg every two weeks or a reduced dose of 150 mg per week. The suitability of the patient for continued dosing and the need for any modification to treatment

schedule (refer to Section 7.7) will be determined by the Investigator (in consultation with the Ionis Medical Advisor as needed) and will be based on factors such as the original rate of decline in the patient’s platelet count, whether any bleeding events were experienced by the patient, and the speed of recovery of platelet count upon holding of dosing.

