If after the first dosing re-challenge the platelet count again falls below 50,000/mm³, then dosing of the patient must be held until the platelet count again returns to at least 100,000/mm³. The suitability of the patient for continued dosing and the need for any further modification to treatment schedule or dose (refer to Section 7.7) will be re-examined by the Investigator (in consultation with the Sponsor Medical Monitor as needed) based on (at least) the factors mentioned above.

If after the second re-challenge the platelet count falls below 50,000/mm³ and is subsequently confirmed (see Section 7.5), dosing with Study Drug will be stopped permanently. The follow-up schedule for any events meeting this stopping criterion will be determined by the Investigator (in consultation with the Sponsor Medical Monitor as needed).

Following rechallenge platelet count should be tested every week until count is stable.

Any unreportable platelet count result must be rechecked and determined not to have met a stopping rule before dosing can continue.

If there is no reportable platelet count within 14 days of the last platelet count, the investigator will contact the patient to hold dosing until a new platelet count is obtained and reviewed.

Definition of Major Bleeding Events^{s3}:

1. Fatal bleeding, and/or
2. Symptomatic bleeding in a critical area or organ, such as intracranial, intraspinal, intraocular, retroperitoneal, intraarterial or pericardial, or intramuscular with compartment syndrome, and/or
3. Bleeding causing a fall in hemoglobin level of 20.0 g/L (1.24 mmol/L) or more within 24 hours, or leading to transfusion of two or more units of whole or red cells

Definition of Clinically Relevant, Non-Major Bleeding Events^{s3}:

1. Multiple-source bleeding
2. Spontaneous hematoma >25 cm²
3. Excessive wound hematoma (not injection site related)
4. Macroscopic hematuria (spontaneous or lasting >24 hours if associated with an intervention)
5. Spontaneous rectal bleeding; epistaxis, gingival bleeding, hemoptysis, hematemesis
6. Bleeding after venipuncture for >5 minutes

Actions in Patients With Low Platelet Count

Platelet count	Dosing Rules	Monitoring Rules
Normal range, >140K/mm ³	No action	Monitor every week unless otherwise specified

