100K/mm ³ - 140K/mm ³	Weekly 300 mg study drug administration	Monitor every 1 week unless otherwise specified Obtain additional lab tests if 2 occurrences of platelet count 100 K/mm ³ -- 140K/mm ³ or 1 occurrence of platelet count ≤ 100K/mm ³ **
75K/mm ³ - 100K/ mm ³	Permanently reduce dose frequency to 300 mg every 2 weeks	Monitor every 1week unless otherwise specified Obtain additional lab tests if 1 occurrence of platelet count ≤ 100K/mm ³ **
50K/mm ³ - 75K/mm ³	If occurs while on dose of 300 mg every 2 weeks or 150 mg every week then permanently discontinue Study Drug, otherwise dose pause. When platelet count returns to >100K/mm ³ restart dosing at dose frequency of 300 mg every 2 weeks or 150 mg weekly ₁ (in consultation with the Ionis Medical Advisor as needed).	Monitor every 2-3 days until two successive values are > 75K/mm ³ then monitor every 1 week Consider discontinuation of antiplatelet/agents/NSAIDS/anticoagulant medication Obtain additional lab tests if 1 occurrence of platelet count ≤ 100K/mm ³ **
≤ 50 K/mm ³	Permanently discontinue Study Drug	Monitor daily until 2 successive values show improvement, then monitor every 2-3 days until 2 successive values are > 75K/ mm ³ . Patient should be evaluated by a hematologist to provide diagnostic and therapeutic management Steroids recommended*. It is strongly recommended that, unless the patient has a medical contraindication to receiving glucocorticoids, the patient receives glucocorticoid therapy to reverse the platelet decline. Monitor triglyceride levels weekly and continue AE monitoring during steroid therapy. Discontinue antiplatelet agents/NSAIDS/anticoagulant medication while platelet count <50K/mm ³ if

		possible Obtain additional lab tests if 1 occurrence of platelet count $\leq 100\text{K}/\text{mm}^3$ **
--	--	---

*Recovery in platelet count may be accelerated by administration of high dose steroids. Treatment guidelines for immune thrombocytopenia (Provan et al. 2010) recommend Dexamethasone 40 mg daily for 4 days every 2-4 weeks for 1-4 cycles; Prednis(ol)one 0.5-2 mg/kg/d for 2-4 weeks then taper; or Methylprednisolone 30 mg/kg/day for 7 days (**note:** may require continuation with oral steroids after methyl prednisolone)

**See Appendix J

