7.8 Withdrawal Criteria

1. **Withdrawal of consent.** A subject wishes to withdraw from the study as stated in the informed consent (all subjects reserve the right to withdraw from the study without prejudice).
2. **Adverse event (or SAE).** The patient develops laboratory test abnormalities that meet any of the stopping rules listed above, or any other adverse event that in the investigator's opinion necessitates withdrawal from the study.
3. **Investigator judgment.** An investigator feels it is in the subject's best interest to terminate participation. The detailed reasoning behind this decision will be documented.
4. **Pregnancy.**
5. **Ineligibility.** Includes study entry criteria violation.
6. **Significant Protocol Deviation.** Includes subject noncompliance or start of an unacceptable concomitant medication.

The reason for discontinuation of study treatment must be recorded in the electronic case report form (eCRF) and source documentation. All efforts will be made to complete and report the observations as thoroughly as possible up to the date of withdrawal. All information, including the reason for withdrawal from study, must be recorded in the eCRF.

Any patient who withdraws consent to participate in the study will be removed from further treatment and study observation immediately upon the date of request. These patients should be encouraged to complete the early termination study procedures and observations at the time of withdrawal. For patients withdrawn for reasons other than withdrawal of consent, every effort should be made to complete the early termination study procedures and observations at the time of withdrawal.

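### The platelet action table in 7.6.3 omits the permanent stop for bleeding: at a confirmed 50,000-75,000/mm³ on 300 mg weekly it says pause, then restart

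*Combined protocol and SAP*

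**What the plan says.** The text of section 7.6.3 gives two rules for a confirmed count below 75,000/mm³, separated by bleeding:

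- A count "that is associated with major bleeding or clinically relevant non-major bleeding" leads to a permanent stop. No dose condition is attached.
- A count "in the absence of major bleeding or clinically relevant non-major bleeding" leads to a temporary suspension until recovery to at least 100,000/mm³. Any further dosing is at 300 mg every two weeks or 150 mg weekly.

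The general re-dosing guidance in 7.5 points the same way: "If any of the stopping criteria described below are met below and are confirmed, the patient will be permanently discontinued from further treatment". Section 7.8, item 2, makes it a reason for withdrawal when "The patient develops laboratory test abnormalities that meet any of the stopping rules listed above".

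The table at the end of 7.6.3, on actions at low platelet counts, has a 50K-75K row that reads: "If occurs while on dose of 300 mg every 2 weeks or 150 mg every week then permanently discontinue Study Drug, otherwise dose pause". Once the count is above 100K, the row says to "restart dosing at dose frequency of 300 mg every 2 weeks" or at 150 mg weekly, consulting the company's medical advisor as needed.

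Section 7.5.3 consists of one sentence, which refers the reader to the table in 7.6.3 for what to do about a reduced count. Section 7.7 requires platelet-related dose adjustments to follow both section 7.6.3 and the table, and does not rank them.

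**The concern.** In the text, bleeding decides between stopping for good and pausing. In the table row, only the current dose decides. A patient on 300 mg weekly with a confirmed count between 50,000 and 75,000/mm³ and a qualifying bleed therefore gets two incompatible instructions from one section.

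The permanent stop exists to protect a patient who has already bled at a low count. A site that manages that patient from the table, as 7.5.3 directs, would resume the drug after platelet recovery. The table lists other permanent stops (50K-75K on reduced dosing, and 50K or below), so a reader could reasonably take its list of stops as complete.

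**Working it through.** No sample size, power or error rate is involved. The check compares the text with the table, case by case.

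**Inputs**

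- Text rules for bleeding and no bleeding below 75,000/mm³: 7.6.3, first paragraph and the suspension paragraph.
- Table rules: 7.6.3 action table, rows 50K-75K and 50K or below.
- Dose states: 300 mg weekly (the target dose in the Precis), or reduced (300 mg every two weeks or 150 mg weekly).

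**Step 1: a confirmed count below 75K with a qualifying bleed.** Two count bands by two dose states give 2 × 2 = 4 cells.

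| Count band | Dose | Text | Table | Agree? |
|---|---|---|---|---|
| 50K-75K | 300 mg weekly | Permanent stop | Pause, restart at reduced dose above 100K | **No** |
| 50K-75K | Reduced | Permanent stop | Permanent stop | Yes |
| 50K or below | 300 mg weekly | Permanent stop | Permanent stop | Yes |
| 50K or below | Reduced | Permanent stop | Permanent stop | Yes |

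The text stops drug in 4 of 4 cells and the table in 3 of 4. They differ in 4 − 3 = 1 cell.

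**Step 2: the same cell without bleeding.** At 50K-75K on 300 mg weekly with no qualifying bleed, the text suspends and may resume at a reduced dose. The table does the same. The row reproduces the no-bleeding rule and applies it to everyone on 300 mg weekly.

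**Step 3: does the table mention bleeding elsewhere?** It has five rows, and none mentions it. Its two notes concern steroid treatment and additional laboratory tests.

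**Step 4: do the holds on dosing close the gap?** Section 7.5 provides that "Patients with initial laboratory test values that reach a stopping rule must not be re-dosed until the re-test results are available", and 7.6.3 adds: "Any unreportable platelet count result must be rechecked and determined not to have met a stopping rule before dosing can continue". Both cover the period before a count is confirmed or reportable. The restart instruction applies after that.

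**Worked case.** A patient on 300 mg weekly has a confirmed count of 60,000/mm³ and spontaneous macroscopic hematuria, which is item 4 of the non-major bleeding definition in 7.6.3. The 7.6.3 text, 7.5 and 7.8 all lead to a permanent stop. The table leads to a pause, then 300 mg every two weeks or 150 mg weekly once the count exceeds 100K. An intracranial bleed (major bleeding, item 2) in the same cell would get the same table instruction.

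**How a patient reaches this cell.** The 75K-100K row already cuts the dose frequency permanently. A patient still on 300 mg weekly would normally have to fall from above 100K to below 75K between weekly counts.

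**The case against.** The strongest reply is that the right rule is already in the protocol. It opens 7.6.3, the suspension rule is expressly limited to patients without bleeding, and 7.5 and 7.8 support the stop. The bleeding definitions sit directly above the table, and 7.5.4 sends anyone classifying a bleed to 7.6.3. Even under the suspension rule, a patient's bleeding history is a factor in deciding whether to resume. Because 7.7 asks for section and table together, one can argue that a permanent stop leaves nothing to restart. On this view the table is simply indexed by count, and the wrong action requires someone to read one cell and miss the rest.

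Most of that is fair. It shows that the stop is intended and that a careful reader would apply it. It does not correct a row that says restart, in a table that 7.5.3 designates as the place to look. Nor would a general rule that the text prevails be safe, because the table is stricter than the text in two cells without bleeding: 50K-75K on reduced dosing, and 25K-50K on 300 mg weekly. There the text suspends and the table stops. Those mismatches are separate from this point, and the fix below does not resolve them.

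It is also fair that one cell in four measures where the rules differ, not how often a patient would be affected. Finally, the restart cell carries a stray subscript with no matching note. It may be an artefact of reading the PDF, but a lost note cannot be excluded.

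**Conclusion.** The concern holds. For a confirmed count of 50,000-75,000/mm³ with major or clinically relevant non-major bleeding on 300 mg weekly, the table omits the text's permanent stop and gives the opposite instruction. For the bleeding rule, the disagreement is confined to that one cell of four, but the cell is at the trial's target dose.

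This is an omission in the table, not a missing rule in the protocol. The situation should be uncommon, the documents give no event frequency, and no effect on the primary comparison is claimed. It should still be corrected, because the table's purpose is to give the right action when such an event occurs.

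The conclusion assumes that the table in 7.6.3 is the one 7.5.3 calls Table 3, and that no note mentioning bleeding was lost when the PDF was read.

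**What to change.** Make the table match the text on bleeding. Insert as the first line of the 50K-75K row, ahead of its existing wording:

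> *Confirmed count with an associated major or clinically relevant non-major bleed (see definitions above): discontinue Study Drug permanently, whatever the current dose. Give no dose while the confirmatory result is pending.*

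Keep the table's permanent stops at 50K-75K on reduced dosing and at 50K or below, and leave the bleeding definitions unchanged.

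The cost is one short entry in one table row. Visits, tests, definitions and sample size stay the same.

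### Section 7.6.3 gives conflicting permanent-stop rules for low platelets: text and table disagree at 25–75K without bleeding, and the 50–75K row omits the bleeding stop

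*Combined protocol and SAP*

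**What the plan says.** All of the rules are in Section 7.6.3. Below, qualifying bleeding means the major and the clinically relevant non-major events defined there, and a reduced regimen means 300 mg every two weeks or 150 mg weekly.

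- **Paragraph 1.** A confirmed count below 75,000/mm³ "that is associated with major bleeding or clinically relevant non-major bleeding" is a permanent stop.
- **Paragraph 2.** A permanent stop also applies "In the event of any platelet count less than 25,000"/mm³, or to a count below 50,000/mm³ "that occurs while the patient is on dosing at 300 mg every two weeks or 150 mg every week".
- **Paragraph 4.** At a confirmed count below 75,000/mm³ without qualifying bleeding, dosing "will be suspended temporarily until the platelet count has recovered to" at least 100,000/mm³. On restarting: "If dosing is continued it should be at a reduced dose frequency of 300 mg every two weeks", or at 150 mg weekly. The investigator decides whether dosing continues.
- **Re-challenge paragraphs.** "If after the first dosing re-challenge the platelet count again falls below 50,000"/mm³, dosing is held until 100,000/mm³ and suitability is looked at again. "If after the second re-challenge the platelet count falls below 50,000"/mm³ and this is confirmed, the stop is permanent.
- **Table, 50–75K row.** "If occurs while on dose of 300 mg every 2 weeks or 150 mg every week then permanently discontinue Study Drug, otherwise dose pause". The row does not mention bleeding.
- **Table, row for 50K and below.** Permanent discontinuation on any regimen.

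Section 7.5.3 sends the reader to the table for the action to take. Section 7.7 requires dose adjustments to follow both Section 7.6.3 and the table, and gives no order of precedence.

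**The concern.** A stopping rule has to give one action for one patient state. Here the same confirmed count on the same regimen can be a permanent stop in one place and a suspension with possible restart a page earlier. A patient at 60K on a reduced regimen, or at 40K on weekly dosing, is off drug for good under the table but may be re-exposed under the text.

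These states are easy to reach on paper. The table's 75–100K row moves a patient permanently to 300 mg every two weeks with no earlier pause, so a first count of 50–75K can already fall in the disputed cell. Platelets are checked every week (Section 6.4.5), so the rule is consulted often. Meeting a stopping rule is also a withdrawal criterion (Section 7.8), so how a patient's participation ends depends on the same ambiguity.

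The bleeding omission is a separate hazard. Someone who follows the pointer in Section 7.5.3 and reads only the 50–75K row would pause and later restart a weekly-dosed patient whom paragraph 1 requires to stop permanently.

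**Working it through.** There is no sample-size or power figure to reproduce. The check sets out the written action for each count band and regimen, taking counts as confirmed.

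**Without qualifying bleeding, 25–75K**

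| Count | Regimen | Text | Table | Result |
|---|---|---|---|---|
| 50–75K | 300 mg weekly | Suspend (para 4) | Pause | Agree |
| 50–75K | Reduced | Suspend (para 4); para 2 stops only below 50K | Permanent stop | **Conflict (a)** |
| 25–50K | 300 mg weekly | Suspend (para 4); para 2 stops only below 25K | Permanent stop | **Conflict (b)** |
| 25–50K | Reduced | Permanent stop (para 2), but hold and reconsider after a first re-challenge | Permanent stop | **Conflict (c), inside the text** |

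Combinations: 2 bands × 2 regimens = 4. Combinations with two written actions: 3. Two of these are text against table; the third is text against text.

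**Threshold gaps, text against table**

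- Reduced regimens: 75,000 − 50,000 = 25,000/mm³.
- Weekly regimen: 50,000 − 25,000 = 25,000/mm³.

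**Why (c) is a conflict.** Paragraph 4 directs any restart to a reduced regimen. A count below 50,000 after the first re-challenge therefore already meets paragraph 2 and the table's lowest row, both permanent stops. The hold, and any second re-challenge that follows from it, cannot happen without breaching paragraph 2.

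**With qualifying bleeding, below 75K**

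- 50K and below, either regimen: text and table both stop permanently.
- 50–75K, reduced regimen: both stop permanently.
- 50–75K, 300 mg weekly: paragraph 1 stops permanently; the table row reads as pause and restart. **Omission (d).**

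**Does another section settle it?** The re-dosing guidance in Section 7.5 makes confirmed stopping criteria permanent in general. That supports paragraph 1 in (d). It cannot settle (a) or (b), because paragraph 4's temporary suspension is itself listed among the stopping rules, and Sections 7.6.2 and 7.6.4 also contain temporary suspensions. Section 7.7 binds the reader to both sources and ranks neither.

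**The case against.** The strongest reply is that the rules can be obeyed together. Section 7.7 is cumulative, and paragraph 4 never requires a restart. Stopping permanently as the table says therefore breaches nothing in the text, while re-dosing breaches the table. Apply the stricter rule and the patient is safe. A cautious investigator could do that in (a) and (b), but no such instruction is written, and an investigator who restarts after recovery is following an express provision. Nor can one source simply be preferred: the table is stricter in (a) and (b), the text in (d).

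A second reply is that paragraph 4, read literally, also covers counts below 25K, where paragraph 2 must override it as the more specific rule; the table rows might override it in the same way. That is a reasonable canon of reading, but paragraph 2 sets its own thresholds for the same regimens and they differ from the table's.

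Some smaller points stand:

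- Item (d) is an omission within a section whose first paragraph states the stop, and it changes the action only on 300 mg weekly.
- Paragraph 4 says a restart should be on a reduced regimen, which is slightly weaker than a prohibition on anything else.
- The text could reach a second re-challenge by another route, through a suspension at 50–75K, though the table forbids it.
- Counting text against table only, the no-bleeding tally is 2 of 4.
- Re-dosing still needs recovery to 100K and the investigator's judgement, and the primary analysis is untouched.

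None of this removes the conflicts.

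**Conclusion.** The concern holds. Without qualifying bleeding, the table stops drug permanently at 50–75K on a reduced regimen and at 25–50K on 300 mg weekly, while the text only suspends. The hold after a first re-challenge contradicts paragraph 2, and the 50–75K row lacks the bleeding stop.

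The consequence is limited to later re-exposure, since dosing halts at once under every reading. The documents give no rate of counts below 75K, so no claim is made about how many patients would be affected or about power. The conclusion rests on the current wording of Section 7.6.3, with counts confirmed as Section 7.5 requires. Because the thresholds govern re-exposure after a recognised safety signal, this should be corrected and not left to interpretation.

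**What to change.** 1. Add to the 50–75K row that qualifying bleeding, on any regimen, means permanent discontinuation. This is needed whichever option is chosen below.
2. Set one permanent-stop threshold for reduced regimens. The safer default is the table's: in paragraph 2 raise 50,000 to 75,000 for those regimens, and limit paragraph 4 to patients on 300 mg weekly with counts of 50–75K.
3. Align paragraph 2's 25,000 threshold for any regimen with the table's row for 50K and below.
4. Delete or rewrite the two re-challenge paragraphs to match.
5. While editing, state that the confirmation step in Section 7.5 applies to the revised thresholds, and assign a count of exactly 50K to one row; it now falls in two.

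If the sponsor and medical monitor prefer the more permissive text, the alternative to steps 2 to 4 is to change the two table rows and reconcile paragraph 2 with the re-challenge paragraphs. Which threshold is right is a clinical judgement; the requirement is that there be only one.

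The cost is a wording amendment to paragraphs 2 and 4, the re-challenge paragraphs and the table, with no extra patients or tests. Under the stricter option, some patients lose the possibility of resuming drug.
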